6.5.2.6. Recording of serious adverse events related to study participation

- Refer to Section [7.2](#) for procedures for the investigator to record SAEs related to study participation. Refer to Section [7.3](#) for guidelines on how to submit SAE reports to GSK Biologicals.
- The subjects/subjects' parent(s)/LAR(s) will be instructed to contact the investigator immediately should the subject manifest any signs or symptoms they perceive as serious.

6.5.3. Procedures during scheduled weekly contacts

Weekly contacts will be home visits (at least every other week) or telephone contacts (TCs). The weekly contact may also be a face to face visit outside the home in certain cases (i.e. at hospital during suspected dengue visit) (**Amended 01 March 2017**)

During the weekly contacts, an adult household member enrolled in the study may respond for all enrolled members of the household. If no adult household member can be reached during the weekly contact (home visit or TC), 3 additional attempts to contact the household will be made on the 3 days following the initial attempted contact (see Section 8.2).

6.5.3.1. Distribution of dengue kits and instruction of subjects/subject's parent(s)/LAR(s) to contact study staff in case of acute febrile illness

Each household will be given at least one dengue kit, which includes one thermometer per subject, study contact information (phone numbers), and diary cards.

- During the weekly contact (home visit or TC), study personnel will ask about AFI (fever [body temperature $\geq 38^{\circ}\text{C}/\geq 100.4^{\circ}\text{F}$] on ≥ 2 consecutive calendar days, measured at least twice, at least 8 hours apart) in the past week and will instruct/remind subject/subject's parent(s)/LAR(s) to contact the study personnel or come to a designated study hospital/clinic for medical evaluation at the occurrence of AFI and solicited symptoms.

6.5.3.2. Collection and verification of diary cards, and recording of diary cards data from diary cards to the eCRF

- During the weekly contact (home visit or TC), a structured check list will be used to inquire about any AFI since the last contact (home visit or TC). Refer to the SPM for the structured check list. This will include inquiring about any hospitalisation that may have occurred and hospitalisation discharge diagnosis for all cases of hospitalisation. If necessary, assistance to complete the diary cards will be provided to the subject/subject's parent(s)/LAR(s). If the subject is hospitalised at the study health care facility, information will be available via the hospital record. Information from both the diary card and hospital/clinic records can be used to update clinical data in the eCRF.
- If a subject or subject's parent/LAR reports fever (body temperature $\geq 38^{\circ}\text{C}/\geq 100.4^{\circ}\text{F}$) during any home visit or TC, the local study coordinator will arrange for a Suspected Dengue First Visit at the designated study hospital/clinic for medical evaluation and blood sampling (refer to Section 6.5.5.1). The Suspected Dengue First Visit should be scheduled within 7 days from the onset of fever (Days 2-7) and should ideally take place on the second day of fever (Day 2). If the visit has not taken place within the 7-day period (Days 2-7) from the onset of fever, it is no longer required and the case will be considered as an undetermined case.
- Collection and distribution of diary cards as needed (only applicable for home visits).
- Recording of diary cards information by the investigator.

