6.4. Outline of study procedures

Table 2 List of study procedures for scheduled visits and contacts

Epoch	Epoch 001		
	Visit 1	Home visits or TCs	Visit 2
Time point	Month 0	Weekly between visits ¹	Month 24
Informed consent (and assent if applicable)	●		
Check inclusion/exclusion criteria	●		
Subject number attribution	○		
Household number attribution	●		
Record socio-demographic data	●		
Record medical history (including history of dengue illness, diagnosis of tuberculosis and JEV vaccination history)	●		
Update medical history			●
Subject card distribution	○		
Distribute dengue kits to subjects/subject's parent(s)/LAR(s), including diary cards to be filled out in case of fever ²	○	○	
Instruct/remind subjects/subject's parent(s)/LAR(s) to contact study staff and to report symptoms in diary card in case of fever ³	○	○	
Contact subjects regarding any AFI and/or hospitalisation ⁴		●	
Collect and verify diary cards (if applicable) ⁵		○ ⁶	○
Record data (solicited symptoms, medication) from diary cards (if applicable)		● ⁶	●
Record SAEs related to study participation	●	●	●
Study conclusion ⁷			●

● is used to indicate a study procedure that requires documentation in the individual eCRF.

○ is used to indicate a study procedure that does not require documentation in the individual eCRF.

AFI: acute febrile illness

eCRF: electronic Case Report Form

JEV: Japanese encephalitis virus

LAR: legally acceptable representative

SAE: serious adverse event

TC: telephone contact

1) Weekly contacts will be home visits (at least every other week) or TCs. ***The weekly contact may be a face to face visit outside the home in certain cases (i.e. at hospital during suspected dengue visit)*** (Amended 01 March 2017)

2) Diary cards will be distributed at the first scheduled visit. A new diary card will be issued by the study staff whenever necessary (i.e., if the subject no longer has one, e.g., the previous one was lost or used).

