Although subjects will be instructed to contact the study staff in the event of AFI (fever [body temperature $\geq 38^{\circ}\text{C}/\geq 100.4^{\circ}\text{F}$] on ≥ 2 consecutive calendar days, measured at least twice, at least 8 hours apart), there may be cases where the subject is taken directly to a hospital/clinic (study or non-study health care facility). If this occurs, a family member should inform the study staff as early as possible, and the study staff should contact the hospital/clinic where the subject is hospitalised. In addition, weekly contacts will also be used to identify subjects who have been hospitalised with AFI where study staff has not been informed. In such case, clinical data will be retrospectively collected in the eCRF. The study physician will be responsible for collecting the retrospective data and informing the local study coordinator for appropriate follow-up.

All subjects with AFI who fail to attend a Suspected Dengue Visit as they were directly hospitalised will be recorded as LCD, non-LCD, or undetermined cases depending on the availability and result of the dengue RT-qPCR test. Refer to the SPM for more information.

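### The weekly contact asks about fever on two consecutive days but acts on any fever, so a subject on fever Day 1 may not be actively asked again until Day 7, 8 or 9

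*Protocol*

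**What the plan says.** **What staff ask.** Protocol Table 2 (section 6.4) lists the weekly task as "Contact subjects regarding any AFI and/or hospitalisation". Section 6.5.3.1 has staff ask about AFI in the past week and spells AFI out as fever on two or more consecutive calendar days. Section 6.5.3.2 adds that "a structured check list will be used to inquire about any AFI since the last contact". The check list itself is in the SPM, which is not among the documents.

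**What staff act on.** The next bullet of 6.5.3.2 opens with "If a subject or subject's parent/LAR reports fever (body temperature" and gives the 38 °C threshold with no two-day condition. The coordinator then arranges a Suspected Dengue First Visit, ideally on Day 2.

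**What subjects are told.** The reminder row of Table 2, which also applies to weekly contacts, tells them "to contact study staff and to report symptoms in diary card in case of fever". The reminder in 6.5.3.1 is instead to call or attend "for medical evaluation at the occurrence of AFI and solicited symptoms". Section 6.5.5.1.1 likewise says "subjects will be instructed to contact the study staff in the event of AFI", and the enrolment instruction in 6.5.2.5 uses the two-day criterion.

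**Who answers.** At the contact, "an adult household member enrolled in the study may respond for all enrolled members of the household".

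**Timing.** Table 4 sets contacts 7 days apart, with 6 to 8 allowed. Section 4.1 requires the PCR sample on Days 2-7 from fever onset. If the visit has not taken place by Day 7, the case is undetermined (Table 4 footnote; 6.5.3.2).

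**The concern.** The question is narrower than the action it feeds. If one member's fever began on the day of the contact, the accurate answer about AFI is no. Unless the fever comes to light some other way, nobody asks again until the PCR window is on its last day or has closed.

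The primary incidence counts subjects with LCD over person-years at risk (Protocol 9.6). Follow-up runs to the first LCD episode or to last contact (Protocol 9.4; SAP 9.2.1). A dengue episode classed as undetermined therefore leaves the numerator while its person-time stays in the denominator, so any bias is downward. The study is meant to supply incidence for efficacy-trial sample sizes (3.1) and to establish case capture for Phase III (1.2), so the weekly question is part of what is being tried out.

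**Working it through.** **Inputs.** Contact interval L = 6, 7 or 8 days (Table 4). Onset is Day 1 and the sampling window is Days 2-7 (4.1, Table 4). Up to three daily retries follow a failed contact (6.5.3).

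**Reproducing the plan's window.** Onset plus 1 day is Day 2 and onset plus 6 days is Day 7, as in Table 4.

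**Day of the next inquiry.** Put a contact on day 0 and fever onset on day k after it (k = 0 to L − 1). At the next contact the fever day is 1 + L − k.

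- For k = 0, the subject on Day 1 at the contact, this is L + 1: Day 7, 8 or 9. Three retries can move it to Day 10, 11 or 12.
- For k ≥ 1 it is Day 2 or later, so a continuing fever meets either question. The two wordings differ only for k = 0.

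**Onset days first picked up too late.** Assume the any-fever question brings every Day-1 fever to a sample by Day 7. Lag is the number of days from contact to sampling.

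| L | Lag | AFI question | Any-fever question | Difference |
|---|---|---|---|---|
| 6 | 0 | 0/6 | 0/6 | 0 |
| 6 | 1 | 1/6 | 0/6 | 1/6 = 16.7% |
| 7 | 0 | 1/7 | 0/7 | 1/7 = 14.3% |
| 7 | 1 | 2/7 | 1/7 | 1/7 = 14.3% |
| 8 | 0 | 2/8 | 1/8 | 1/8 = 12.5% |
| 8 | 1 | 3/8 | 2/8 | 1/8 = 12.5% |

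At L = 8 with same-day sampling, onset on the day after a contact (k = 1) is first asked about on Day 8 under either wording.

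**Upper bound.** Let s be the share of LCD cases that depend on active inquiry. Suppose onsets are spread evenly over the interval and every contact-day onset precedes the contact. At L = 7 the loss is then at most s/7 of LCD cases. If only half of contact-day onsets precede the contact, it is s/14 (7.1% of s). The documents do not give s.

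**Against the planned precision.** Take the 40-case row of Table 17. The rate is 40/3300 × 100 = 1.21 per 100 person-years. With design effect 2.6 the half-width is 1.96 × √(2.6 × 40)/3300 × 100 = 0.61, giving 0.61 to 1.82 as printed. The extreme s = 1 would remove at most 40/7 = 5.7 of 40 cases, or 5.7/3300 × 100 = 0.17 per 100 person-years.

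**The case against.** The strongest reply is that other routes cover a Day-1 fever, and much of it stands.

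- **The words put to households are unseen.** The protocol gives the topic of the check list and refers to the SPM for the list. If the list already asks about any fever, the gap does not exist in practice. This stands, and the point is conditional on it.
- **Volunteered fever is covered.** The second bullet of 6.5.3.2 acts on fever reported at any home visit or telephone contact, and its Day 2 target fits a Day-1 report. This stands, but one adult may answer for everyone and has been asked only about two-day fever.
- **The reminder comes on the day of onset.** A subject reminded at that contact can self-report from the next day and be sampled on Days 2-7. This stands for everyone who follows the reminder.
- **Diary cards can reveal the fever.** A card is started on the first day of fever (6.5.2.5, 6.6), and 6.5.3.2 offers help with it at home visits and telephone contacts alike. The limit in "Collection and distribution of diary cards as needed (only applicable for home visits" concerns handling of the cards and does not remove this chance of disclosure. Help is given only if necessary, so disclosure is possible rather than assured.
- **Direct hospitalisation with a PCR result** still allows an LCD classification (4.3, 6.5.5.1.1).

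These routes narrow the gap to a small group. They do not make the question match the action. Active contact also serves to find illness that nobody reported: 6.5.5.1.1 uses it that way for hospitalised AFI.

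**Conclusion.** The mismatch and the Day 7, 8 or 9 timing hold. This is a minor gap in active inquiry. It affects only subjects who do not volunteer the fever, do not self-report on Days 2-7 despite the reminder, do not reveal it through diary-card help, and are not hospitalised with a PCR result. It also requires that the SPM check list does not already ask about any fever.

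Any bias in LCD incidence is downward, of unknown and probably small size. At the 7-day interval the bound is s/7, under even onsets, contact-day onsets preceding the contact, and full sampling of disclosed Day-1 fevers. At the 6-day interval it is zero if the sample is taken on the day of the next contact.

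A reader might infer that one dengue case in seven is lost, or that the primary rate is understated by 0.17 per 100 person-years. The documents support neither. Both figures need s = 1, meaning that no case comes through self-report, although the protocol instructs self-report at enrolment and at every weekly contact. Nothing in the documents shows that any case is lost.

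**What to change.** In Table 2, 6.5.3.1 and 6.5.3.2, and in the SPM check list if it does not already do so, ask for each enrolled household member about *any fever (≥38 °C) since the last contact, including today*. This matches the action bullet in 6.5.3.2.

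Keep the two-day AFI criterion for case classification and study blood draws. Existing rules handle a Day-1 fever found this way: 6.5.3.2 arranges the visit, ideally on Day 2, and 6.5.5.1.1 bars study blood on Day 1 and has the subject return next day if fever persists.

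Aligning the reminder is optional. If 6.5.3.1 is changed to tell subjects to call for any fever, change the instructions in 6.5.2.5 and 6.5.5.1.1 too, so that no new mismatch arises.

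**Cost.** The change is to a few lines of wording, plus coordinator follow-up of one-day fevers that resolve. Enrolment had already begun by Amendment 3, so a mid-study change would alter ascertainment within a single incidence estimate; its date should be recorded and reported.

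**Limit.** Rewording does not rescue the second late onset day at an 8-day interval.

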6.5.3.3. Recording of serious adverse events related to study participation

- Refer to Section 7.2 for procedures for the investigator to record SAEs related to study participation. Refer to Section 7.3 for guidelines on how to submit SAE reports to GSK Biologicals.
- The subjects/subjects' parent(s)/LAR(s) will be instructed to contact the investigator immediately should the subject manifest any signs or symptoms they perceive as serious.

6.5.4. Procedures at scheduled Visit 2

The close-out visit (Visit 2) will take place at home or at the hospital/clinic.

6.5.4.1. Update medical and JEV vaccination history

Update medical history, including tuberculosis diagnosis and JEV vaccination.

6.5.4.2. Collection and verification of diary cards, and recording of diary cards data from diary cards to the eCRF

- Collection and recording of diary card if needed.
- Recording of SAEs related to study participation.

6.5.4.3. Recording of serious adverse events related to study participation

Refer to Section 6.5.2.6.

6.5.5. Procedures at Suspected Dengue Visits**6.5.5.1. Procedures at Suspected Dengue First Visit*****6.5.5.1.1. Important general remarks***

All study subjects with AFI (fever [body temperature $\geq 38^{\circ}\text{C}/\geq 100.4^{\circ}\text{F}$] on ≥ 2 consecutive calendar days, measured at least twice, at least 8 hours apart) should be seen at a designated study hospital/clinic by the study physician. The Suspected Dengue First Visit should be scheduled within 7 days from the onset of fever (Days 2-7) and should ideally take place on the second day of fever (Day 2).

If a subject with fever (body temperature $\geq 38^{\circ}\text{C}/\geq 100.4^{\circ}\text{F}$) on ≥ 2 consecutive calendar days, measured at least twice, at least 8 hours apart has not been evaluated at a Suspected Dengue First Visit (or directly in a hospital/clinic) within the 7-day period (Days 2-7) from the onset of fever, the Suspected Dengue First Visit is no longer required and the case will be considered as an undetermined case. If a diary card has been filled, the data needs to be recorded in the eCRF.

Blood samples for study procedures should not be drawn from subjects who attend a study healthcare facility on the first day of fever (body temperature $\geq 38^{\circ}\text{C}/\geq 100.4^{\circ}\text{F}$), i.e., on Day 1. Medical assistance can be provided to these subjects but they will be asked to come back the following day should the fever persist. Blood samples for study procedures should only be drawn from the second day of fever (i.e., from Day 2, the second calendar day with fever) and onwards, up to Day 7.

Although subjects will be instructed to contact the study staff in the event of AFI (fever [body temperature $\geq 38^{\circ}\text{C}/\geq 100.4^{\circ}\text{F}$] on ≥ 2 consecutive calendar days, measured at least twice, at least 8 hours apart), there may be cases where the subject is taken directly to a hospital/clinic (study or non-study health care facility). If this occurs, a family member should inform the study staff as early as possible, and the study staff should contact the hospital/clinic where the subject is hospitalised. In addition, weekly contacts will also be used to identify subjects who have been hospitalised with AFI where study staff has not been informed. In such case, clinical data will be retrospectively collected in the eCRF. The study physician will be responsible for collecting the retrospective data and informing the local study coordinator for appropriate follow-up.

All subjects with AFI who fail to attend a Suspected Dengue Visit as they were directly hospitalised will be recorded as LCD, non-LCD, or undetermined cases depending on the availability and result of the dengue RT-qPCR test. Refer to the SPM for more information.

6.5.5.1.2. Physical examination

A detailed physical examination to assess the subject's general condition and any dengue associated clinical signs/symptoms as well as relevant clinical signs/symptoms will be performed (see [Table 5](#)). Collected information needs to be recorded in the "Suspected Dengue First Visit" section of the eCRF.

Table 5 Physical examination during Suspected Dengue First Visit

Physical examination (all subjects)	
 body temperature and route, height and weight, cardiac and respiratory rates, blood pressure, dengue-like rash, abdominal tenderness liver enlargement > 2 cm, tourniquet test (positive/negative), only pertains to subjects ≥ 5 years of age (Amended 01 March 2017) haemorrhagic manifestations; petechiae, bleeding from mucosa, gastrointestinal tract, injection sites or other locations, Injected pharynx, clinical signs of plasma leakage: oedema, pleural effusion, ascites
Additional information (subjects with severe disease and suspected Dengue Shock Syndrome [DSS] - according to investigator's judgement)	
 narrow pulse pressure (< 30 mm Hg) hypotension cold, clammy skin restlessness

Treatment of any condition observed during the physical examination will be performed according to local medical practice.

6.5.5.1.3. Record medical history

Update medical history in the eCRF (in relation to what was encoded during the Suspected Dengue First Visit).

6.5.5.1.4. Blood sampling

Blood samples should only be drawn in case of AFI (i.e., fever [body temperature $\geq 38^{\circ}\text{C}/\geq 100.4^{\circ}\text{F}$] on ≥ 2 consecutive calendar days, measured at least twice, at least 8 hours apart) during the Suspected Dengue First Visit from the second day of fever (i.e., from Day 2, the second calendar day with fever) and onwards, up to Day 7.

The following blood samples should be collected unless an obvious alternative diagnosis, i.e., an obvious cause of fever other than dengue, has been identified and is documented (Amended 01 March 2017):

- Whole blood for laboratory confirmation of dengue by NS1-antigen (ICT test and/or ELISA): 0.5 mL, from all subjects (any age). The results of this/these test(s) should be recorded in the eCRF.
- Whole blood for laboratory confirmation of dengue infection by (generic and/or serotype-specific) RT-qPCR: 2.5 mL, from all subjects (any age).

- Whole blood for haematology assessment (complete blood count): 2 mL, from all subjects \geq 5 years of age and from subjects $<$ 5 years of age only if clinically indicated, as per investigator judgement or local recommendations. The results of these tests should be recorded in the eCRF.
- Whole blood for other tertiary (research) endpoints related tests (including, but not limited to, neutralising antibody against JEV and Chikungunya virus, tissue culture to isolate infectious agents, and sequencing to characterise infectious agents): **3.5 mL**, from all subjects \geq 18 years of age. A subset of these samples will be tested.

6.5.5.1.5. Collection and recording of solicited symptoms from diary card

- During the Suspected Dengue First Visit, the diary card (partially completed) is reviewed by the physician and data recorded in the “solicited symptoms” section of the eCRF if the subject meets AFI criteria. Refer to the Section [6.6](#) for a description of the solicited symptoms to be recorded.
- After the Suspected Dengue First Visit, the subject/subject’s parent(s)/LAR(s) continues to complete the diary card until resolution of all symptoms. If necessary, assistance to complete the diary cards will be provided to the subject/subject’s parent(s)/LAR(s).
- Once completed, the diary card is collected and the data are reviewed with the subject and encoded in the eCRF, either by the physician during a Return or Suspected Dengue Follow-up Visit at hospital/clinic or by the study staff during a home visit.

6.5.5.1.6. Recording of serious adverse events related to study participation

Refer to Section [6.5.3.3](#).

6.5.5.2. Procedures at Return Visit (optional)

Based on the physician’s assessment during the Suspected Dengue First Visit, a **Return Visit** may be needed and will be conducted as directed as per local medical practices.

A Return Visit is a visit linked to the Suspected Dengue First Visit and should take place if the subject’s physical condition necessitates medical evaluation, according to local medical practice. The investigator will determine whether this Return Visit is necessary and whether it is considered as part of the same episode.

- Update physical examination: medical data related to any suspected dengue case will be collected for hospitalised study subjects and for those followed in the outpatient setting at the Return Visit. Diagnostic and treatment intervention will be conducted as per local medical practices.
- Verify diary cards and record any new data in the eCRF.
- Record any SAEs related to study participation. Refer to Section [6.5.3.3](#).

6.5.5.3. Procedures at Suspected Dengue Follow-up Visit

All AFI cases need to be followed up until resolution of fever (body temperature $\geq 38^{\circ}\text{C}/\geq 100.4^{\circ}\text{F}$) and/or resolution of symptoms and signs are reported. The signs and symptoms should be recorded on the **Suspected Dengue Follow-up (convalescent) Visit** page of the eCRF or on the weekly contact page (in case of home visit). This information may be collected during a home visit by medically trained member of the study personnel.

- Verify diary cards and record any new data in the eCRF.
- Record any SAEs related to study participation. Refer to Section **6.5.3.3.**

